4. STUDY POPULATION

4.1 Population (base)

All women under the age of 40 diagnosed with cancer for whom a fertility preserving cancer treatment is applied will be eligible for inclusion.

[figure not shown]

Fig. 1: Most common cancer in women 15–39 years old. *Incidence rates per 100,000.(6,7)

[figure not shown]

Fig. 2:

Model-based cumulative probabilities of first post diagnosis parenthood. For the young adult diagnostic age group, the curves represent conditional cumulative probability of parenthood given the patient had no children at age 20. The dashed line represents siblings and the solid line represents cancer patients.(8)

4.2 Inclusion criteria

Histological proven cancer in women up to 40 years old but in their fertility years with a wish to preserve their fertility by undergoing fertility preserving cancer treatment.

4.3 Exclusion criteria

A potential subject who meets any of the following criteria will be excluded from participation in this study:

- Mentally disabled or significantly altered mental status that would prohibit the understanding and giving of informed consent.

5. METHODS

5.1 Randomisation, blinding and treatment allocation

n.a.

5.2 Study procedures

For this study, it will not be necessary to postpone diagnostic procedures or treatment. Participation in this study does not influence normal treatment.

5.3 Withdrawal of individual subjects

Subjects can leave the study at any time for any reason and if they wish to do so this will be without any consequences. The investigator can decide to withdraw a subject from the study for urgent medical reasons.

5.4 Replacement of individual subjects after withdrawal

n.a.

5.5 Follow-up of subjects withdrawn from treatment

n.a.

5.6 Premature termination of the study

No reasons for premature termination of the study are anticipated.

6. STATISTICAL ANALYSIS

We plan to use descriptive statistics (mean +/- standard deviation), two-sided tests, and Wilcoxon rank sum test to compare continuous variables in two groups, for more than two groups, the Kruskal-Wallis exact test will be used. For comparing a proportion with an expected value, a binominal exact test will be used. Results are considered significant at $P < .05$.

Analysis will be performed with SAS (version 9.2) and Statistical Package for Social Sciences for Windows (version 16). Statistical analysis will be performed under supervision of Prof. [name] (Leuven Cancer Institute, Belgium).

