Regarding cancer of the female genital tract, in which radical surgery is mostly the standard, alternatives are being investigated to preserve fertility. There are still a lot of gaps in research regarding these fertility sparing surgical treatments and the interventions are often experimental, as there is no standardized technique available due to lack of data. This leads to many different strategies being applied among different centers. In addition, there is a lack of studies investigating the oncological safety and obstetric outcome of these fertility sparing treatment protocols. Another major consequence of the absence of a standard technique is the difficulty to inform patients about the best treatment.

It is important to obtain a significant amount of cases in order to make a thorough study especially since several types of cancer do not occur regularly. It is in this respect that this study aims to fill the gap in current research.

The purpose is to enable us to obtain a significant amount of data to create more standardized fertility sparing treatment protocols and to better inform clinicians and patients on the efficacy of fertility sparing cancer treatment.

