3. STUDY DESIGN

The proposed research concerns a multicenter prospective observational cohort study. European collaboration is utilized in order to include sufficient number of patients.

This is a study, for which primary approval was granted by UZ Leuven. UZ Leuven is the initiator of the study and the ethical committee of UZ Leuven is the central ethical committee. The UZ Leuven protocol is used in all centers, including the international collaborators.

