3.3 Sample size

We aim for at least 500 cases per tumour type + 1 control patient per study patients (resulting in 500 control patients per tumour type). This is a minimum that allows us to calculate the oncological prognosis (secondary objective).

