9. ADMINISTRATIVE ASPECTS, MONITORING AND PUBLICATION

9.1 Handling and storage of data and documents

The investigator records clinical data, using a paper or electronic case report form (CRF), all data is collected in an online database that is available through www.cancerinpregnancy.org, such database being the ownership of Sponsor. Participating physicians have a personal account to log in to the registration page and access the electronic CRF. They will have permanent access only to their own series of patients. The participating physician ensures the confidentiality, accuracy, completeness, legibility and timeliness of the data recorded. Data handling and statistical analysis will be done anonymously by the investigator, with the subject identification code list only available to the local investigator (and research nurse if applicable) working in the local center. The code will be based on the birth date and center abbreviation (and not patient initials). The investigator will be the owner of the data. Data will be kept for 20 years.

Sponsor, participating physicians and sites agree and commit to handle and protect the data in accordance with the terms and provisions of all applicable data protection rules and legislation including the Belgian law of 08 December 1992 on Privacy Protection in relation to the Processing of Personal Data and the Belgian law of 22 August 2002 relating to patient's rights.

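### Section 6 fixes tests that make no allowance for centre, although the comparison is non-randomised, strategies differ among centres, and controls are not tied to the centre of their case

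*Protocol*

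**What the plan says.** Section 6 of the protocol lists its tests by name. For two groups it gives "two-sided tests, and Wilcoxon rank sum test to compare continuous variables in two groups"; beyond that, "for more than two groups, the Kruskal-Wallis exact test will be used". For one group against a reference, "For comparing a proportion with an expected value, a binominal exact test will be used". The threshold is a P value below .05. No stratification, centre term or clustered variance appears.

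On the setting:

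- Section 3: "The proposed research concerns a multicenter prospective observational cohort study".
- Section 2, on the lack of a standard technique in fertility-sparing surgery: "This leads to many different strategies being applied among different centers". The Summary says much the same of fertility-sparing treatment in general.
- Section 3.1: the primary objective compares oncological outcome with a control group; the secondary objective compares obstetrical and neonatal outcome with the general population.
- Section 3.3: "We aim for at least 500 cases per tumour type + 1 control patient per study patients". Section 3.4 repeats the one-to-one rule. Neither says that the control must come from the same centre as the case.
- Section 5.1: randomisation is not applicable.
- Section 9.1: "The code will be based on the birth date and center abbreviation".

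**The concern.** Every test named in Section 6 takes its null distribution from independent observations, and the binomial test also needs one common probability. The protocol's rationale gives a reason to doubt this. If centres treat differently, and if treatment strategy affects outcome, women from one centre will tend to resemble each other.

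Two things are then at stake. The first is bias: without randomisation or a centre link for controls, a centre that contributes mainly cases or mainly controls carries its own case mix and practice into the treatment contrast. Recruiting 500 + 500 women does not shrink that. The second is the error rate: a variance computed as if the women were independent is too small when the groups sit in different centres, or when there is only one group.

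**Working it through.** **The plan's own figure.** The 500 + 500 per tumour type cannot be reproduced, because no effect size, event rate, power or precision target is given. It serves below only as the number of women.

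**Inputs from the protocol:** tests and threshold (Section 6); 500 cases and 500 controls, one to one (Sections 3.3 and 3.4); several centres (Section 3).

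**Assumed inputs:** women per centre m = 10 to 50 and ICC = 0.01 to 0.05. The protocol states neither, nor the number of centres.

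**Step 1. Single group, or arms drawn from separate centres.**

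Design effect DE = 1 + (m − 1) × ICC. Effective n = 500 / DE. Actual two-sided error = 2 × (1 − Φ(1.96 / √DE)).

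| m | ICC | DE | Effective n of 500 | Error at nominal 5% |
|---|---|---|---|---|
| 10 | 0.01 | 1 + 9 × 0.01 = 1.09 | 459 | 6.0% |
| 10 | 0.05 | 1 + 9 × 0.05 = 1.45 | 345 | 10.4% |
| 25 | 0.02 | 1 + 24 × 0.02 = 1.48 | 338 | 10.7% |
| 50 | 0.01 | 1 + 49 × 0.01 = 1.49 | 336 | 10.8% |
| 50 | 0.05 | 1 + 49 × 0.05 = 3.45 | 145 | 29.1% |

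**Step 2. Each centre supplies equal numbers of cases and controls.** The centre effect cancels in the difference, and DE is about 1 − ICC, that is 0.95 to 0.99. The unstratified test is then at or slightly below 5%.

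**Step 3. Simulation of the Wilcoxon test.** There were 1,000 women, about 500 per group, with a normal random centre effect, no treatment effect and 3,000 runs per setting. In the uneven mix, each centre's share of cases was drawn uniformly between 0 and 1.

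| m | ICC | Arms in separate centres | Uneven mix | Balanced within centre |
|---|---|---|---|---|
| 10 | 0.01 | 0.057 | 0.046 | 0.049 |
| 10 | 0.05 | 0.088 | 0.058 | 0.046 |
| 50 | 0.01 | 0.096 | 0.069 | 0.055 |
| 50 | 0.05 | 0.285 | 0.137 | 0.040 |

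Simulation error is about 0.004 near 0.05 and up to 0.008 for the largest value. The separate-centre column follows the formula of Step 1 and lies slightly below it in each row.

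**Step 4. Smaller centres.** With m = 3, ICC 0.01 gives DE = 1.02 and ICC 0.02 gives DE = 1.04, for errors of 5.2% and 5.5%. Analyses are per tumour type and some of these cancers are rare, so clusters of this size are possible.

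**Step 5. Which case applies.** For two groups, the protocol does not settle the spread of cases and controls over centres, so any column of Step 3 is open. For the comparison with the general population, the exact binomial test is the method in Section 6 that fits. There is no control arm from the same centres, so Step 2 cannot apply and any positive ICC raises the error.

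**The case against.** The strongest objection is that handling of centre is usual SAP content, and the SAP is not at hand. That would answer a protocol that left its tests open. Section 6 does not: it names specific unstratified tests and a threshold. The point rests on what is fixed there, together with controls not linked to centre, and not on missing detail.

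Four other objections stand in part.

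- The protocol says that strategies differ among centres. It does not say that outcomes correlate within them. That is an inference, though a reasonable one, since the study assumes that strategy matters for outcome.
- Inflation in the two-group tests needs an uneven split over centres. One-to-one inclusion does not secure balance, but neither does it imply separation.
- The Wilcoxon test is named for continuous variables, whereas oncological outcome is recurrence and survival. The remedy must therefore apply to whichever test is used for the outcome.
- If strategy varies by centre, adjusting for centre may absorb part of what the registry wants to learn. Strategies can still be described by centre. The contrast of fertility-preserving with standard treatment should not carry centre differences unnoticed.

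A reader might also infer that the planned confidence intervals are too narrow. The document does not support this: Section 6 plans descriptive statistics, tests and a P threshold, and no intervals.

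**Conclusion.** The concern holds as a conditional one. Section 6 makes no allowance for centre in a non-randomised multicentre comparison whose controls are not tied to centre.

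- **Uneven spread of cases and controls:** centre can be mixed with treatment. Under the assumed ICC and m, the error of a nominal 5% test is about 5% to 14%, rising to about 6% to 29% only if the arms come from wholly separate centres.
- **Balanced within centres:** about 5% or slightly below (simulated 0.040 to 0.055), with some loss of precision.
- **Comparison with an expected proportion:** anti-conservative under any positive ICC, about 6% to 29% over the assumed range.

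Smaller centres give less in every case. It would be tempting to conclude that all P values in this study are wrong, or that 29% is the likely error. Neither follows: balance keeps the rank test about nominal, and 29% is the upper end of an assumed range.

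**What to change.** In Section 6, state that case-control comparisons are stratified by centre (by country where centres are small) or fitted with a random centre effect, whichever test or model is used for the outcome. For a proportion compared with an expected value, replace the plain exact binomial test with a method that allows for clustering by centre.

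The cost is analysis wording. Some P values become less favourable. Centres that supply only one group contribute little to a stratified test; a random effect keeps them in. Centre is already part of the patient code (Section 9.1), so no new data item is needed. For retrospective records collected anonymously (Section 8.2), the sponsor should confirm that the centre part of the code is kept.

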3.1 Objectives

Primary Objective:

To record the incidence and oncological outcome when a fertility preserving cancer treatment is applied in young women and compare the oncological outcome with a control group.

Secondary Objective(s):

To record the incidence and fertility outcome when a fertility preserving cancer treatment is applied in young women and compare the obstetrical and neonatal outcome with the general population.

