3.4 Study procedures

In women younger than 40 years old with a cancer diagnosis for whom a fertility preserving treatment is applied, the most important oncological data will be registered, as well as information on the fertility and oncological outcome. Control patients are women who are younger than 40 years of age diagnosed with cancer and who received standard treatment. All types of cancer and all types of treatment will be registered. Patients can be included both prospectively and retrospectively. For every study patient, we include one control patient.

Recruitment of patients:

Because information on pregnant state is not available in most cancer registries prospective recruitment of patients is done as followed networking (e.g. INCIP), newsletters, presentation at conferences for obstetricians, oncologists, haematologists, and also a website for professionals (www.cancerinpregnancy.org) and for patients (<http://www.uzleuven.be/kanker-en-zwangerschap>).

We will collect the following data:

At baseline:

Oncological data include type of cancer, the date of diagnosis, tumour histology, stage of the disease, the type of treatment, cancer recurrence and survival.

Fertility data include gravidity and parity, menstrual pattern after cancer treatment, conception (artificial or natural), obstetrical complications, gestational age at delivery and mode of delivery (induction, caesarean section, spontaneous labour).

Paediatric data that will be collected include birth weight, gender, congenital malformations, admission to neonatal care unit and reason of admission.

Annually until end of study:

We will request information from the treating physician regarding patient's health status (pregnant yes/no, relapse yes/no, site of relapse, treatment of relapse, date of relapse, date of death if applicable).

This study does not involve any direct input or effort from the patient. Only the collection of existing information through the medical records is aimed for.

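### Section 6 names no test that fits the primary comparison of recurrence and survival between cases and controls, and Section 3.3 labels that objective secondary

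*Protocol*

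**What the plan says.** Protocol 3.1 sets as primary objective to record the oncological outcome and "compare the oncological outcome with a control group". Its only secondary objective concerns fertility outcome, with obstetrical and neonatal outcome set against the general population.

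Protocol 3.4 lists recurrence and survival among the oncological data. Status is updated "Annually until end of study" and includes "date of relapse, date of death if applicable". Entry is mixed: "Patients can be included both prospectively and retrospectively". The control group is fixed in number only: "For every study patient, we include one control patient". No matching on diagnosis date or length of follow-up is stated. Section 5.3 lets women leave at any time, and Section 8.2 allows some retrospective records to be collected anonymously and without follow-up.

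Protocol 6 names a "Wilcoxon rank sum test to compare continuous variables in two groups", the Kruskal-Wallis exact test for more than two groups, and one method for proportions: "For comparing a proportion with an expected value, a binominal exact test will be used". Its mention of two-sided testing gives sidedness, not a method.

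Protocol 3.3 justifies 500 cases and 500 controls per tumour type with: "This is a minimum that allows us to calculate the oncological prognosis (secondary objective"; the parenthesis closes there.

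**The concern.** The primary comparison uses relapse and death dates from women followed for different lengths of time, so those without an event are censored at different times. The rank tests in Section 6 make no allowance for censoring. The binomial test compares one sample with a fixed value, so it does not compare two sampled groups. The only two-group test that the protocol names therefore does not suit its primary objective.

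The summary justifies the study by the lack of data on oncological safety. In that setting a comparison with low power can be read as reassurance, and one that mistakes unequal follow-up for unequal prognosis can err in either direction.

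The label in 3.3 is a separate matter. It leaves the protocol with two answers on which objective is primary, in the sentence that justifies the sample size.

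**Working it through.** **The plan's own figure.** The 500 + 500 per tumour type cannot be reproduced or refuted: the protocol gives no event risk, effect size, power or follow-up length. The figures below take 500 per group and two-sided 5% from the protocol. Event risks and follow-up are assumptions.

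**Step 1: fit of each named test.**

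| Named in Section 6 | Suits | Cases v controls on relapse and death? |
|---|---|---|
| Wilcoxon rank sum, Kruskal-Wallis | uncensored continuous data, e.g. birth weight, gestational age | No: no handling of censoring |
| Exact binomial | a proportion against a fixed population value | No: one sample, ignores follow-up time |

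**Step 2: power when follow-up is spread equally in both groups.** Exponential times, control hazard −ln(1−p)/5 with 5-year risk p = 5%, 10%, 20%. The case hazard is doubled, so case 5-year risks are 1−(1−p)² = 9.75%, 19%, 36%. Follow-up is uniform over 1-9 years, with 4,000 simulated trials per setting (the comparison of proportions was run separately, with 1,500).

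| Analysis | p = 5% | 10% | 20% |
|---|---|---|---|
| Wilcoxon on all observed times | 16% | 45% | 92% |
| Wilcoxon on time to relapse, relapsed women only | 5% | 6% | 10% |
| Two-group comparison of relapse proportions | 81% | 98% | 100% |
| Log-rank | 83% | 98% | 100% |

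If every woman had exactly 5 years of follow-up, Wilcoxon on all observed times would give 84/98/100%, the same as log-rank, so its loss comes from the spread of follow-up. The relapsed-only version sees almost nothing because it discards the difference in counts. At p = 10% there are on average 50 v 93 relapses, but median times to relapse of 2.58 v 2.46 years.

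**Step 3: false positives when follow-up differs between groups.** No true difference, assumed 5-year risk 20%, 2,000 simulated trials for the rank and log-rank tests.

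| Follow-up, cases v controls (years) | Wilcoxon, all observed times | Wilcoxon, relapsed only | Log-rank |
|---|---|---|---|
| 1-10 v 1-10 | 4.2% | 4.7% | 4.7% |
| 1-9 v 1-10 | 52% | 11.6% | 4.9% |
| 1-7 v 1-10 | 100% | 63% | 5.6% |

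**Step 4: relapse proportions in the Step 3 settings.** With hazard λ = −ln(0.8)/5 = 0.0446 and follow-up uniform over a to b years, the expected share relapsed is 1 − (e^(−λa) − e^(−λb)) / (λ(b−a)): 21.2% for 1-10 years, 19.6% for 1-9, 16.1% for 1-7.

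- 1-9 v 1-10: difference 1.66 points, standard error √(2 × 0.204 × 0.796 / 500) = 2.55 points, ratio 0.65. The chance of rejection is Φ(0.65 − 1.96) + Φ(−0.65 − 1.96) ≈ 10%.
- 1-7 v 1-10: difference 5.14 points, standard error √(2 × 0.187 × 0.813 / 500) = 2.46 points, ratio 2.09. The chance of rejection is about 55%; simulation gave about 53%.

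The two errors run in opposite directions. Shorter follow-up of cases makes them look worse when observed times are ranked, and safer when relapse proportions are compared.

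**Step 5: the label.** 3.1 lists one secondary objective: fertility, obstetrical and neonatal outcome. The oncological prognosis in 3.3 can therefore only be the item that 3.1 calls primary. No assumption is needed for this.

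**The case against.** The strongest reply is that Section 6 contains no wrong statement. It gives the rank tests to continuous variables and the binomial test to comparisons with an expected value. Both uses are sound for data the protocol collects. It never applies either to relapse or survival and never calls its list complete. Survival methods are commonly left to a statistical analysis plan, which may exist.

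Much of this stands. A reader might infer that the protocol plans an invalid Wilcoxon analysis of survival, or that the rates above are what the study will produce. The text supports neither: the rates show what would follow if the only named two-group test were used. A reader might also infer that the binomial test will be run with the observed control rate as its expected value, which would give a type I error near 16%. Section 6 does not direct that either.

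It is also fair that, with equally spread follow-up, the rank test loses power but keeps its error rate, and that a plain comparison of relapse proportions would lose almost nothing. Section 6 names no two-group test of proportions, however, and Step 4 shows that it too fails once follow-up differs. The protocol states no such difference, but nothing in it secures equal follow-up.

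What does not stand is that this is only missing detail. The protocol has a section that chooses tests by name, and the choice serves the secondary objective and leaves the primary one without a fitting method. No analysis plan can remove the contradiction between 3.1 and 3.3 while both texts remain. That contradiction is a slip in one label; no error allocation or power figure in the document depends on it, and it does not show the sample size to be wrong.

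**Conclusion.** The point holds in this form: Section 6 fixes tests suited to the secondary objective and names none suited to the primary one, a two-group comparison of recurrence and survival under open-ended, unequal follow-up. It should be fixed. It does not show that the planned analysis is invalid.

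The size depends on what would be done in practice. Ranking observed times would cost much power against a doubled hazard at low event risks, and less at 20%. A one-year difference between the groups in maximum follow-up would raise its false-positive rate from 5% to about 50%. These sizes rest on assumed risks, exponential times and assumed follow-up. The mismatch between tests and objective rests on the text alone, as does the contradiction between 3.1 and 3.3.

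**What to change.** In Section 6, state that recurrence-free and overall survival are compared between cases and controls, per tumour type, by Kaplan-Meier curves and a Cox hazard ratio with 95% confidence interval. Time runs from diagnosis, women are censored at last contact, and the model adjusts for the stage and histology already collected. Keep the rank tests for uncensored continuous variables and the binomial test for comparisons with a fixed population value. Censor retrospective records without follow-up at the last date in the record. Handle delayed entry, for women who had to be event-free at inclusion, as a sensitivity analysis or in the statistical analysis plan. Correct the label in 3.3 to agree with 3.1.

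The cost is a last-contact date and an inclusion date per woman, a little more analysis, and wording in two sections. Diagnosis, relapse and death dates are already collected, and no extra patients are needed. Adjustment reduces confounding by choice of treatment but does not remove it.

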1. SUMMARY

Rationale:

Cancer is the second leading cause of death during the reproductive years. The long term survival improves for most cancers, reaching 80% for pediatric cancer and more than 70% for cancers in adults between 20 and 49 years of age. Early detection and improvements in cancer treatment contribute to these figures. As a result, quality of life of which preservation of fertility is one aspect, becomes more important. Fertility may however be influenced by surgery and by the gonadotoxic effects of chemo and/or radiotherapy. Therefore, fertility sparing treatments are offered to young patients in order to maintain the wish to conceive after cancer treatment. This however is associated with deviation of standard treatment and many different strategies are applied among different centers. In addition, there is a lack of studies investigating the oncological safety of these fertility sparing treatment protocols. The results of this study will enable us to better inform clinicians and patients on the efficacy of fertility sparing cancer treatment.

Objective:

To record the incidence, treatment and long term follow up of fertility preserving cancer treatment. Both the oncological and fertility outcome are recorded.

Study design: International multicentre prospective observational trial

Study population: All female adults with a cancer for whom a fertility preserving cancer treatment is applied. The results of the study population are compared to young women undergoing standard cancer treatment.

Intervention (if applicable): n.a.

Main study parameters/endpoints:

Registration of cancer diagnosis, treatment and outcome. Both the oncologic and fertility outcome are registered.

Nature and extent of the burden and risks associated with participation, benefit and group relatedness:

All patients receive fertility sparing cancer treatment on their specific request. Participation in this observational registration study is not associated with burdens or risks, since participation will not alter the treatment regimens.

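### The primary oncological comparison is non-randomised and unmatched, yet Section 6 names only unadjusted methods, so a stage imbalance within a tumour type could make fertility-sparing treatment look safer than it is

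*Protocol*

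**What the plan says.** Protocol Section 3 describes a "multicenter prospective observational cohort study", and Section 5.1 marks randomisation and allocation as not applicable. The Summary says of the cases: "All patients receive fertility sparing cancer treatment on their specific request". The primary objective in Section 3.1 is to record oncological outcome and "compare the oncological outcome with a control group".

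On controls, Section 3.4 says "Control patients are women who are younger than 40 years of age diagnosed with cancer and who received standard treatment" and "For every study patient, we include one control patient". Section 3.3 adds "We aim for at least 500 cases per tumour type + 1 control patient per study patients". Sections 3.2 to 3.4 name no matching variable other than tumour type. They do not require a control to have been a candidate for fertility-sparing treatment. Section 3.4 allows both prospective and retrospective inclusion.

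The oncological items in Section 3.4 include type of cancer, date of diagnosis and "tumour histology, stage of the disease, the type of treatment, cancer recurrence and survival". Age at diagnosis is not in the list.

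Section 6 names descriptive statistics, two-sided tests of no stated kind, the "Wilcoxon rank sum test to compare continuous variables in two groups", Kruskal-Wallis for more than two groups, and an exact binomial test of a proportion against an expected value. Significance is set at 0.05.

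**The concern.** When treatment is chosen, the two groups can differ in prognosis before treatment begins. Stage is the obvious candidate, because it may bear both on who is offered or requests a fertility-sparing approach and on recurrence. The protocol deals with this neither in its design (no matching or restriction within tumour type) nor in its analysis (no regression, stratified, weighted or survival method). The variables needed are collected but are given no role.

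If cases have earlier disease than controls, a crude comparison credits the treatment with the benefit of the earlier stage. That errs towards reassurance on the primary question. Section 2 says the results are meant to inform clinicians and patients and to support more standardised treatment protocols, so the error would reach counselling. A larger sample does not help; it only makes the biased estimate more precise.

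**Working it through.** **The plan's own figure.** The 500 + 500 per tumour type comes with no event rate, effect or power, so it cannot be reproduced. For scale, at two-sided 0.05 and 80% power, 500 against 500 detects 10% against 16.0%, or 20% against 27.5% (assumed control rates). That is a difference of about 6 to 8 points.

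**Inputs.** From the protocol: 500 per group, two-sided 0.05. Assumed, because the protocol gives none: recurrence of 5% (early stage) and 25% (later stage), the stage mixes below, and a simple two-proportion test standing in for an unadjusted comparison of recurrence.

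**Formulas.**
- Crude rate = RR × (share early × early rate + share later × later rate), with RR = 1 for controls.
- SE = √[p₁(1−p₁)/500 + p₂(1−p₂)/500].
- Chance of significance in the direction of the difference = Φ(|p₁−p₂|/SE − 1.96).

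**Large imbalance: 90% of cases and 60% of controls early.**
- Controls: 0.6 × 5% + 0.4 × 25% = 13%.
- No effect. Cases: 0.9 × 5% + 0.1 × 25% = 7%. Crude ratio 7/13 = 0.54. SE = 0.0189; Φ(0.06/0.0189 − 1.96) = **89%** falsely in favour of cases.
- True doubling in each stage. Cases: 14% against 13%. SE = 0.0216; Φ(0.01/0.0216 − 1.96) = **7%** power to show harm.

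**Mild imbalance: 80% and 70% early.**
- Controls: 0.7 × 5% + 0.3 × 25% = 11%.
- No effect. Cases: 0.8 × 5% + 0.2 × 25% = 9%. SE = 0.0190; Φ(0.02/0.0190 − 1.96) = about **18%** falsely in favour of cases.
- True doubling. Cases: 18% against 11%. SE = 0.0222; Φ(0.07/0.0222 − 1.96) = about **88%** power.

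**Lower rates (3% and 15%), same order.** 67%, 5%, 12% and 66%.

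**Does adjustment recover the answer?** Expected counts with a true within-stage ratio of 1.5, rates 5% and 25%, crude test against a stage-stratified Cochran-Mantel-Haenszel test:

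| Early stage, cases / controls | Crude rates | Crude ratio (p) | Stratified ratio (p) |
|---|---|---|---|
| 70% / 70% | 16.5% / 11.0% | 1.50 (0.012) | 1.50 (0.008) |
| 80% / 70% | 13.5% / 11.0% | 1.23 (0.23) | 1.50 (0.013) |
| 90% / 70% | 10.5% / 11.0% | 0.95 (0.80) | 1.50 (0.029) |
| 90% / 60% | 10.5% / 13.0% | 0.81 (0.22) | 1.50 (0.029) |

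Stratifying on one variable already on the form restores the true ratio in each row.

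**The case against.** **A statistical analysis plan may supply the adjustment.** Choice of covariates and model is often left to one, and it is not at hand. This lowers the certainty that the final analysis will be crude. However, Section 6 does not defer to another document. It lists methods, none adjusts, and the design does not compensate.

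**Section 6 does not actually assign a crude test to the primary contrast.** This is correct. A reader might infer that the protocol commits to an unadjusted test of recurrence, but Wilcoxon and Kruskal-Wallis are for continuous variables, and the binomial test compares with an expected value rather than with controls. Only the unspecified two-sided tests could apply. The defect is that no suitable method is named and all named methods are unadjusted. The proportion test above illustrates a crude analysis; it is not the protocol's stated one.

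**The bias depends on how controls are picked.** Also correct. One might conclude that the problem exists whatever the control selection, but matching or restriction on stage, histology and period would remove the imbalance modelled here. The point rests on none being stated.

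**Tumour type is handled.** The target of equal numbers per tumour type balances it by design, so the gap lies within tumour type.

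**A crude analysis need not hide or reverse harm.** With the mild imbalance a doubling is usually detected. A significant reversal appears only further out in the assumed range: 90% against 50% early with a true ratio of 1.5 gives 10.5% against 15.0%, ratio 0.70, p = 0.033. The protocol gives no stage distribution, so it does not support a claim that harm would be reversed, or even that cases do have earlier disease.

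**Conclusion.** The concern holds as a gap in how the primary comparison is planned: a non-randomised, unmatched contrast for which every named method is unadjusted and none suits recurrence or survival between cases and controls. If cases have the better stage mix within a tumour type, the bias runs towards apparent safety. Under the 5% and 25% assumptions its size runs from moderate (about 18% false significance, with a doubling still seen at about 88% power, but a true ratio of 1.5 diluted to 1.23) to severe (89% false significance and 7% power to see a doubling). All rates and stage mixes are assumptions. What the documents establish is the absence of any stated control for confounding within tumour type, not the amount of confounding that will occur.

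**What to change.** In Section 6, state that within each tumour type the primary comparison is an adjusted time-to-event analysis. One example is a Cox model for recurrence and another for death, with stage, histology, age at diagnosis and year of diagnosis as covariates; overlap weighting on the same variables is an alternative. Report the crude result beside it. A time-to-event method is needed because annual follow-up to the end of study, combined with prospective and retrospective entry, gives unequal observation times, which an adjusted binary regression would ignore.

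In Section 3.4, add age at diagnosis to the baseline items. Sites must already know it to apply the age criterion.

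The cost is some wording, slightly more analysis and possibly a somewhat wider interval than the crude one. The other covariates are already collected. Adjustment will not remove confounding by factors that are not recorded, and the report should say so.
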